### 6.2 General Methodology

Descriptive statistics will be used for group characteristics and outcomes. Mean, standard deviation, median, and range will be described for the continuous variables and frequency and percentage for categorical variables. Intergroup comparisons considering baseline characteristics will be done using Fisher's exact test for

dichotomous variables, Chi-square test for non-ordered categorical variables, and the Mann-Whitney U-test for continuous variables.

The comparative analyses between the groups considering the dichotomous study outcomes will be performed using logistic regression adjusted for known and statistically identified confounders (variables that are related both to the study group and the outcome). Odds-ratios (OR) with associated 95% CI, p-values and area under the receiver operating characteristic curve (AUC-ROC) will be presented. Hosmer-Lemeshow test will be performed as a goodness-of-fit test.

The comparative analyses between the groups considering the continuous study outcomes will be performed using linear regression adjusted for known and statistically identified confounders. Model assumptions will be checked by reviewing diagnostic plots, and if needed transformation (e.g. log) of the outcome variable will be performed. Least square means with associated 95% CI, p-values and  $R^2$  will be presented.

Outcome variables length of stay in ICU (hours) and length of hospital admission (days) will be handled as continuous variables in the case of no censored patients. In case of censored patients in the database, time to discharge will be studied using Cox proportional hazard model, resulting in hazard ratios (HR) with 95% CI and p-value. Proportional hazards assumptions will be checked graphically. Otherwise, the variables will be studied as continuous variables using either linear regression assuming normal distribution if applicable or Poisson or negative binomial regression depending on the distribution of the variables. Results from the Poisson and negative binomial regression result in risk ratio (RR) with 95% CI and p-value.

Time to all-cause mortality will be investigated by using Cox proportional hazard model, describing HR with 95% CI and associated p-value following adjustment. Event rates, the number of events divided by total number of follow-up time will be described, together with the 95% CI obtained using exact 95% Poisson confidence limits. Graphically, this variable will be described applying Kaplan-Meier technique.

The confirmatory analyses will be performed for the following outcome variables, applying Bonferroni-Holm adjustment to minimize the Type I error:

- The primary composite outcome variable, death at 30 days and/or severe bleeding (according to GUSTO bleeding criteria) within 7 days after treatment
- The secondary outcome variable all-cause death at 30 days post-intervention
- The secondary outcome variable severe bleeding (according to GUSTO bleeding criteria) within 7 days after intervention
- The secondary outcome variable difference in RV/LV-ratio as compared before and after treatment

Additionally, the sensitivity analyses will be conducted applying adjustment for propensity score (PS) and PS 1:1 matching for the confirmatory analyses listed above, using the patients' background data to estimate the PS, performed by using logistic regression. Matching will be made applying nearest neighbour matching with the optimal caliper width of 0.2 of the standard deviation of the logit of the PS, as recommended. The performance will be validated by comparing the patient characteristics between the matched groups, that are expected not to differ, and described by standardized mean difference. The potential selection bias in the PS 1:1 matching will be examined in a drop-out analysis comparing included vs excluded FlowTriever® cases.

All non-confirmatory analyses will be evaluated in an exploratory manner at significance level of 0.05. All analyses will be performed using SAS software version 9.4 or later (SAS Institute Inc., Cary, NC, USA).

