## 3 Study Design

This is a national multicenter retrospective observational study including patients with acute PE treated between 2021 and 2023 with FlowTriever® in Sweden, to evaluate safety and effects of treatment with the FlowTriever® device. Treated patients will be compared to patients treated with thrombolysis, in the respective hospital during the time period when FlowTriever® has been in use.

Eligible patients will be identified through screening of the relevant clinics/databases at each participating center for:

- Treatment code(s) for thrombolysis and/or pulmonary thrombectomy
- Diagnosis code(s) for pulmonary embolism and/or pulmonary angiography

Data from patients who have been treated for suspected, but not verified, PE may be collected for descriptive purposes but excluded from comparative analyses.

Data will be collected through review of patient records, and subsequently anonymized, organized and analyzed. Collection, handling, and storage of data will be done in accordance with the General Data Protection Regulation (GDPR).

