## 5.6 Confounders and Predictors

The confounders and predictors for the outcomes will be used in propensity scores and adjustments. All variables listed below will be included when building propensity scores. For the adjusted analyses, only the

strongest confounders and predictors will be part of the analyses. The number of confounders/predictors in the adjusted analyses will be based on the number of events available in the studied cohort. The general recommendation is to not have more than 1 variable/10 events in a statistical model. We will calculate the maximum number of variables in our study as N events/10.

The following variables will be investigated whether they are statistically defined confounders, i.e. related to both the intervention and the outcome:

- Contraindication for thrombolysis (8 categories)
- Insufficient previous effect of thrombolysis
- Cardiac arrest before treatment

The following variables will be investigated for their relation to the study outcomes:

- Age
- Sex
- Active cancer
- Invasive ventilation before treatment
- Circulatory instability
- Chronic heart failure
- Chronic pulmonary disease (COPD, asthma, other)
- Respiratory rate >30 beats/min
- Center

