## 6.5 Primary Analyses

The primary analysis will be performed using logistic regression adjusted for known and statistically identified confounders. OR with associated 95% CI, p-values and AUC-ROC will be presented. Hosmer-Lemeshow test will be performed as a goodness-of-fit test.

The sensitivity analysis of the primary variable will be performed by using:

- 1) Adjustment for PS
- 2) PS 1:1 matching – in case match to at least 70% of FT patients is found

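### The primary model's confounders are chosen from the study data by a rule with no stated threshold, so real confounders can be dropped from the confirmatory odds ratio

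*SAP*

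**What the plan says.** SAP Section 6.5: "The primary analysis will be performed using logistic regression adjusted for known and statistically identified confounders". Section 6.2 repeats this and defines the second kind as "statistically identified confounders (variables that are related both to the study group and the outcome".

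Section 5.6 has two lists. For contraindication to thrombolysis (8 categories), inadequate effect of earlier thrombolysis and cardiac arrest before treatment it says: "The following variables will be investigated whether they are statistically defined confounders, i.e. related to both the intervention and the outcome". For age, sex, active cancer, invasive ventilation, circulatory instability, chronic heart failure, chronic pulmonary disease, high respiratory rate and center it says: "The following variables will be investigated for their relation to the study outcomes". Only the strongest enter the adjusted models, and their number is capped at events divided by ten. Section 7 puts this investigation in Table 3, on the full analysis set, which also supplies the primary p-value.

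The SAP does not say which confounders count as known, what p-value or other criterion decides that a variable is related, or how strength is measured. Section 5.6 puts every listed variable into the propensity score without screening, but Sections 6.2 and 6.5 use the score only for sensitivity analyses.

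**The concern.** Section 5.4 gives contraindication and unsuccessful thrombolysis as examples of why FlowTriever is used. They help determine treatment, so whether they confound depends on how patients were selected and on prognosis. It does not depend on whether a test in about 260 patients detects a relation with outcome. An outcome screen that fails for lack of power removes the variable although the groups remain unbalanced on it, and the imbalance then passes into the treatment odds ratio. The confidence interval takes no account of the selection.

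The rule is also open. Two analysts could follow the SAP faithfully and fit different primary models, each chosen after seeing the outcomes. The result at stake is one of the four confirmatory comparisons under Bonferroni-Holm, in a non-randomised study where confounding by indication is the main threat.

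**Working it through.** **1. The plan's own figure.** Section 6.1 gives 60 and 200 patients, 20% and 40% event rates, a two-sided Fisher's exact test and alpha 0.05. Power = Σᵢ Σⱼ Bin(i; 60, 0.20) · Bin(j; 200, 0.40) · 1[Fisher p ≤ 0.05] = 82.7%. The stated minimum of 80% holds. It is an unadjusted calculation and serves here only as a source of sizes.

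**2. Room in the model.** Planned events: 0.40 × 200 + 0.20 × 60 = 80 + 12 = 92, so 92/10 allows about 9 terms. With 40% in both groups: 0.40 × 260 = 104, so about 10. The SAP counts variables, not parameters. An 8-level factor uses 8 − 1 = 7 parameters. (Section 5.4 lists none plus eight other entries; if none is a separate level, it is 8.) Contraindication alone could fill most of the allowance.

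**3. What dropping one confounder does.** Assumptions, since the SAP gives no such figures: no treatment effect, contraindication in 60% of FlowTriever and 12% of thrombolysis patients, outcome OR 2, 40% events in the thrombolysis group. Let p be the risk without contraindication and q the risk with it, where q/(1−q) = 2p/(1−p).
- 0.88p + 0.12q = 0.40 gives p ≈ 0.380, q ≈ 0.550.
- FlowTriever risk = 0.40 × 0.380 + 0.60 × 0.550 ≈ 0.482.
- Crude OR = (0.482/0.518)/(0.40/0.60) ≈ 1.40, where the true value is 1.

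**4. How often it is dropped.** Simulation with the same assumptions, 60 versus 200: screen contraindication on group and outcome, keep it if both tests pass, then take the Wald test of group. The 8 categories are none plus seven types. Ranges are over repeated runs. With 2,000 data sets the standard error is √(0.05 × 0.95/2000) ≈ 0.5 points at 5% and √(0.10 × 0.90/2000) ≈ 0.7 points at 10%.

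| Handling of contraindication | Kept | Type I error (nominal 5%) | Median OR |
|---|---|---|---|
| 8-category screen, 0.05 | 35–38% | 9.2–10.3% | 1.20–1.21 |
| 8-category screen, 0.10 | not reported | 7.8% | not reported |
| 8-category screen, 0.20 | not reported | about 6–7% | not reported |
| Yes/no screen, 0.05 | 66% | 4.6–5.2% | 1.06–1.07 |
| Forced in as yes/no | always | 4.4–5.4% | 0.99 |

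For the 8-category screen at 0.05 with other imbalances: 60% versus 12% gives 7.5% at OR 1.5 and 8.9% at OR 3; 40% versus 10% gives 5.5–8.0% over OR 1.5–3; 80% versus 10% at OR 2 gives 16.6%, median OR 1.35. At the first Holm step (0.05/4 = 0.0125), the base case gives 3.5%, against 1.1% when forced in.

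**5. Several yes/no confounders acting in the same direction.** For prevalence 20% versus 30%, a two-way 0.05 screen keeps a true confounder in 11%, 25% and 35% of data sets at outcome OR 1.5, 2 and 3. For 20% versus 40% it keeps 25%, 59% and 83%.

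| True confounders | Screen | Type I error, screened | Type I error, all forced in |
|---|---|---|---|
| 1 | 0.05 | 4.2–5.8% | 4.2–5.8% |
| 3 | 0.05 | 5.6–7.0% | 4.2–5.8% |
| 6, all two-way | 0.05 | 8.2–8.8% | 5.1–6.0% |
| 12, split as in Section 5.6 | 0.05 | 12.1–14.3% | 5.1–6.0% |
| 12 | 0.20 | 5.5–7.0% | 5.1–6.0% |

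The forced-in ranges are joint for 1 or 3 and for 6 or 12 confounders. The events/10 cap and the strongest-only rule were not simulated, so the rows for twelve are illustrative.

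**The case against.** **The rule is not a significance filter on both sides.** A reader might infer that a confounder enters only if it is significant for both group and outcome. The SAP does not say that: its wording admits known confounders without a test, never mentions significance at this step, and screens nine of the twelve variables on outcome only. This stands. It does not protect the primary model, because no known confounder is named and the obvious ones are on the screened list.

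**Inflated error is not a general result.** A reader might infer that the primary test always exceeds 5%. It does not. With one yes/no confounder there is no clear excess, and most of the excess in the contraindication example comes from the 8-category coding: the same 0.05 screen on a yes/no variable gives about 5%. This stands, and the size must be stated conditionally.

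**The direction in the example is against FlowTriever.** A median OR of 1.2 makes the device look worse, while the Section 2 hypothesis is that it is better. The example shows bias, not a false claim of benefit.

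**The propensity score analyses use everything.** They are reported beside the main result in Table 4.1, so a gap left by dropped confounders could show there. That is real mitigation, but the confirmatory result is still the screened model.

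**Center.** One might read "patients treated with thrombolysis, in the respective hospital" in Section 3 as promising a within-hospital analysis. It describes where comparators are drawn from, so leaving center among the screened predictors contradicts nothing.

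**Conclusion.** The point holds as a defect of specification with conditional consequences. The primary adjustment set is left to data-driven selection with no threshold, no measure of strength and no named known confounders, and the variables closest to the treatment decision are among those that can be lost.

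How much harm follows depends on choices that the SAP leaves open. In the assumed contraindication scenario, type I error ranges from about 5% to about 10% and the median OR from about 1.07 to 1.2, according to coding and threshold alone. It rises further with stronger imbalance or with many confounders in one direction under a strict screen, and nearly vanishes with a lenient threshold. All prevalences, outcome odds ratios and thresholds are assumptions. The loss of real confounders is the firmer conclusion; the error-rate figures show what can happen, not what will. The SAP should be changed on this point before the data are analysed.

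**What to change.** Before the data are analysed, name the primary adjustment set in Sections 5.6 and 6.5 on subject-matter grounds:

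- Include contraindication to thrombolysis as yes/no and cardiac arrest before treatment.
- State how patients with inadequate effect of earlier thrombolysis are handled. Section 3.2 excludes the prior-thrombolysis subgroup from formal comparison, while Section 5.6 lists inadequate effect as a candidate covariate.
- Add the other listed predictors in a fixed order until the events/10 limit is reached, counting parameters. The two variables above plus the eight predictors other than center, one parameter each, make 2 + 8 = 10, against an allowance of about 9 or 10. Center costs the number of centers minus one, so its place in the order must be stated too.
- Delete selection from the data and the undefined reference to known confounders, and keep Table 3 as description.

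The cost is a change of SAP wording and a slight loss of precision if a covariate proves unimportant. The propensity score sensitivity analyses can stay as they are.

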## 2 Study Objective and Hypothesis

The objective of this study is to evaluate catheter-directed intervention with the FlowTriever® device by comparison to contemporary systemic thrombolysis in patients with acute PE.

The hypothesis is that patients treated with the FlowTriever® device will have lower incidence of the primary outcome variable, the composite endpoint death at 30 days and/or severe bleeding (according to GUSTO bleeding criteria) within 7 days after treatment, than patients treated with contemporary thrombolysis.

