### 5.5.2 Secondary Outcome Variables

The secondary variables in this study are:

- Difference in RV/LV-ratio as compared (up to 48h) before, and (up to 48h) after, treatment. RV/LV-ratio before treatment will be assessed on CT, and after treatment on echocardiography.
- Difference in pulmonary artery pressure (systolic, diastolic and mean) as compared (up to 48h) before and (up to 48h) after treatment.
- Incidence of severe bleeding (according to GUSTO bleeding criteria) within 7 days after treatment
- Type of bleeding (severe, moderate, mild GUSTO)
- Intracranial bleeding (yes, no)
- Incidence of all-cause death at 30 days after treatment
- Time to all-cause death within 30 days after treatment
- Causes of death in patients treated with FlowTriever® vs thrombolysis
- Occurrence of cardiac arrest before (within 24 hours), during, or after (within 24 hours) treatment
- Occurrence of rescue treatment with thrombolysis, ECMO, or surgical thrombectomy
- Length of stay in ICU or IMU (hours)
- Length of hospital admission (days)

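### The length-of-stay rule does not say how in-hospital death enters; on its likely default branch, a group with more early deaths appears to have the shorter stay

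*SAP*

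**What the plan says.** SAP 5.5.2 lists two stay outcomes among the secondary variables: ICU or IMU stay in hours, and hospital admission in days. SAP 6.2 gives them a two-way rule.

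- **No censoring.** The stays "will be handled as continuous variables in the case of no censored patients", analysed "using either linear regression assuming normal distribution if applicable or Poisson or negative binomial regression depending on the distribution of the variables".
- **Censoring present.** "In case of censored patients in the database, time to discharge will be studied using Cox proportional hazard model".

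Neither section defines censoring for these outcomes, and neither mentions patients who die before discharge. No competing-event, survivors-only or death-ranked analysis of stay is planned. Thirty-day death is a secondary outcome in its own right ("Incidence of all-cause death at 30 days after treatment") and part of the primary composite. Under 6.2 and 6.3 the stay outcomes lie outside the Bonferroni-Holm set and are tested in an exploratory manner at 0.05.

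**The concern.** The data come from patient records, for patients treated up to the end of 2023 (SAP 3 and 3.1). By the time of review almost every stay has ended, by discharge or by death. Read literally, nobody is then censored and the continuous branch applies. A patient who dies on day 1 contributes a stay of one day, which the model cannot tell apart from a very quick recovery.

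If early mortality differs between the groups, that difference carries over into stay with the wrong sign for interpretation: the group that loses more patients early looks more efficient. If FlowTriever has fewer early deaths, it appears to prolong stay. If confounding by indication gives it more early deaths, it appears to shorten stay. Adjusting for baseline confounders removes only the part of the mortality gap that those variables explain. What remains still feeds into stay, and it would be reported with an estimate, confidence interval and p-value.

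**Working it through.** **Figures in the plan.** The SAP states no figure for stay or mortality. Its only relevant numbers are in 6.1: 60 FlowTriever and 200 thrombolysis patients, and composite rates of 20% and 40%. Exact two-sided Fisher power for these is 82.7%, consistent with the stated minimum of 80%. The group sizes are therefore used as given. The composite rates are not death rates and are not used as such.

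**Assumed inputs.**
- Survivor stay is the same in both groups: log-normal, median 8 days, log SD 0.6. The mean is L = 8 × exp(0.6²/2) = 8 × 1.197 = 9.58 days.
- Stays ended by death average D = 3 days.
- Death risks are p_F (FlowTriever) and p_T (thrombolysis).

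**Size of the shift.** Mean stay in a group is (1 − p)L + pD, so

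FlowTriever minus thrombolysis = (p_T − p_F)(L − D) = (p_T − p_F) × 6.58 days.

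- 5-point gap: 0.05 × 6.58 = 0.33 day
- 10-point gap: 0.10 × 6.58 = 0.66 day
- 15-point gap: 0.15 × 6.58 = 0.99 day
- 20-point gap: 0.20 × 6.58 = 1.32 days

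The sign follows the mortality gap, provided L exceeds D, that is, provided deaths come earlier than a typical discharge.

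**How often it reaches p < 0.05.** Simulation with 60 vs 200 patients, exponential death times, and an unadjusted two-sample test on raw and log stay:

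| Deaths, FlowTriever vs thrombolysis | Shift (days) | Rejection, raw | Rejection, log |
|---|---|---|---|
| 30% vs 30% | 0 | about 5% | about 5% |
| 15% vs 20%, 10% vs 15% | 0.3 | 6–8% (both scales) | 6–8% (both scales) |
| 20% vs 30% | 0.7 | 12% | 16% |
| 15% vs 30% | 1.0 | 19% | 32% |
| 10% vs 30% | 1.3 | 29% | 53% |

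The last row depends a little on how late death times are generated: variants give 1.3–1.4 days, 28–33% raw and 53–57% log. If deaths average 6 days instead of 3, the 15% vs 30% case shrinks to 0.15 × (9.58 − 6) = 0.54 day, with about 9% (raw) and 13% (log) rejection.

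**The Cox branch.** Same survivor stay, deaths at about 2 days, risks 20% vs 40%. Hazard ratios are FlowTriever vs thrombolysis; below 1 means slower discharge.

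- Death counted as discharge: HR 0.80, rejection 30%.
- Death censored (cause-specific hazard of live discharge): HR 1.00, rejection 5%.
- Death kept in the risk set (subdistribution hazard): HR 1.57, rejection 75%.

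On the same data the log-linear model rejects in 58% of runs. An unstated rule therefore decides between slower discharge, no difference and more frequent discharge. The value of 1.00 arises partly because the simulation makes potential stay unrelated to the risk of death.

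**The case against.** Several counter-arguments have force.

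- **The continuous branch is conditional.** For an event called discharge, a patient who dies undischarged is a natural candidate for censoring, and in complete records that may be why the Cox branch exists. This is a fair reading, but 6.2 does not state it. The continuous branch is the likely default, not a certainty.
- **A reader might infer that the Cox branch fails as well.** The SAP does not support that. Censoring deaths gives the cause-specific hazard of live discharge, and rejection then stays close to nominal (5–7% in most runs, at most 7.7%). The problem persists only if death is counted as discharge. What the branch lacks is a stated rule and the cumulative incidences beside it.
- **A reader might infer that the trial expects a mortality difference.** SAP 2 says "patients treated with the FlowTriever® device will have lower incidence of the primary outcome variable", and that variable is a composite of death and severe bleeding. The 40% and 20% in 6.1 belong to the composite, and much of the expected gain could be in bleeding.
- **The larger artefacts need large gaps.** At 5 points the excess nearly vanishes. The simulation is also unadjusted, whereas the plan adjusts.
- **Rejection is not strictly a false positive.** Mean bed use really does differ in these scenarios. The error lies in reading that difference as an effect on recovery or discharge.
- **The consequence is limited.** The outcomes are exploratory, and 30-day death and time to death are reported alongside.

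These points limit the reach and size of the concern. They do not supply the missing rule.

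**Conclusion.** The point holds as a gap in a stated analysis rule. Followed literally on complete records, 6.2 scores an early death as a short stay, and the group with more early deaths then looks better on stay. The direction follows from arithmetic as long as deaths precede typical discharge. That is plausible for hospital stay but less certain for ICU or IMU stay, where survivors may also leave early; the sizes above were worked out for hospital stay only.

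The size rests wholly on assumed mortality, stay and death times. It runs from about 0.3 day and near-nominal rejection at 5-point gaps to about 1.0–1.3 days, with 19–29% (raw) or 32–53% (log) rejection, at 15–20-point gaps. A firm claim that FlowTriever will be made to look worse would go too far: the SAP states no death rates, and the artefact can run either way. No confirmatory conclusion is affected.

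**What to change.** In SAP 6.2, replace the two-way rule for both stay outcomes:

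1. Make time to discharge alive (from hospital, and from ICU or IMU) the comparative analysis, with in-hospital death as a competing event. Report the adjusted cause-specific hazard ratio, together with the cumulative incidence of live discharge and of death by group.
2. State that a patient who dies is neither counted as discharged nor entered as a completed stay, and reserve censoring for stays whose end is not recorded.
3. Keep raw stay as a description, shown separately for survivors and for patients who died.

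Days alive and out of hospital, or out of ICU or IMU, to day 30 could be added as an optional supplement. This measures something different and is a matter of preference.

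The cost is a few sentences of SAP text. Stay and time to death are already study outcomes, so no new data are needed. The small downside is a hazard ratio in place of a difference in days.
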